2.6 Analysis supporting secondary objectives

Not applicable

2.6.1 Secondary endpoint(s)

The secondary objectives in this study are to assess efficacy, safety and tolerability of crizanlizumab 5.0 mg/kg in SCD subjects.

The following secondary efficacy endpoints will be analyzed on all FAS subjects who have completed 26 and 52 weeks on treatment to evaluate clinical efficacy of crizanlizumab 5 mg/kg:

- a. The rate of priapic events by 26 and 52 weeks of treatment.
- b. The percent reduction from baseline in acute priapic events (defined as an unwanted, painful erection that lasts more than 4 hours and need a visit to emergency room) by 26 and 52 weeks of treatment. Note that, this analysis will only be performed if an adequate number of subjects are present.
- c. The rate of uncomplicated VOC events (defined as an acute event of pain with no known cause for pain other than a vaso-occlusive event; and requiring treatment with a parenteral or oral opioids or other parenteral analgesic; but is NOT classified as an acute chest syndrome, hepatic sequestration, splenic sequestration or priapism and these events will not be adjudicated) by 26 and 52 weeks of treatment. Events include both healthcare and self-reported events.
- d. The rate of complicated VOCs (defined as acute chest syndrome, hepatic sequestration, splenic sequestration, and acute priapism) recorded by healthcare visit, by 26 and 52 weeks of treatment.

The efficacy endpoints will be assessed and summarized by 26 weeks and by 52 weeks .

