### 10.1.2 Protocol exempt AEs & SAEs

Protocol Exempt AEs & SAEs are implemented in the crizanlizumab program. VOCs must be reported on the VOC page in the eCRF. As VOCs are considered secondary endpoints for the purpose of evaluation of efficacy, AEs and SAEs involving VOCs SHOULD NOT be reported as AEs or SAEs for the purpose of this study. These events will not be considered as SAEs in regard to reporting requirements. Procedures which are directly related to the VOC, e.g. ventilation of a patient with acute chest syndrome are considered part of the VOC and will not be reported as AE/SAEs but entered in the CRF-page "concomitant non-drug therapies/procedures". Additional events or complications which are not VOCs itself will be reported as AE/SAEs. Details will be given in the CRF-completion guidance. In case that new information arises which changes the diagnosis of a VOC, i.e. gives another medically determined explanation than vaso-occlusion in the opinion of the investigator, the event has to be reported according to the rules of [Section 10.1](#) and must be reported to Novartis within 24 hours of learning of the new information.

The events in [Table 10-1](#) will not be reported as AEs/SAEs.

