**Table 10-1 List of Events Not Requiring AE/SAE Reporting**

#### VOC Events

- Uncomplicated sickle cell-related pain crisis (SCPC) or vaso-occlusive crisis (VOC)\*
- Acute chest syndrome
- Hepatic sequestration
- Splenic sequestration
- Acute priapism requiring a visit to a medical facility

\*VOC is defined as pain crises (defined as an acute onset of pain for which there is no other medically determined explanation other than vaso-occlusion and which requires therapy with oral or parenteral opioids or parenteral NSAIDs) as well as other complicated crises, such as acute chest syndrome, acute priapism, and hepatic or splenic sequestration.

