2.2 Analysis sets

The analysis sets to be used are defined as below.

All efficacy analyses will be performed on subjects in FAS who have completed treatment. The Safety Set will be used for all the safety analysis.

Full Analysis Set (FAS)

The FAS include all enrolled subjects to whom the study treatment has been assigned regardless of whether or not they have received at least 1 dose of study treatment or have at least 1 post-baseline assessment.

Safety Set (SAF)

The SAF will consist of all subjects who received at least 1 dose of study treatment.

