2.6.2 Statistical hypothesis, model, and method of analysis

Similar analyses on percent reduction in acute priapic events for subjects from full analysis set will be conducted, as done for primary endpoint.

Annualized rates will be calculated for the secondary endpoints.

The annualized rate of events is defined as the total number of events for a subject occurring from the date of initial infusion to the last contact date of the Treatment Phase of the study x 365.25 divided by the number of days during that same time period. This calculation accounts for early dropouts or lost to follow-up by extrapolating the priapism events rate of every subject to 1 year.

Annualized events rate = Total number of events x 365.25 / (end date – treatment start date +1), where end date is defined as the minimum of (last dose date until treatment discontinuation + 27 days, date of initiation or discontinuation of HU/HC or L-glutamine - or other therapies to treat SCD and or to prevent/reduce VOCs such as voxelotor and erythropoietin, cut-off date).

Descriptive summary statistics including n, mean, standard deviation (SD), lower quartile (Q1), median, upper quartile (Q3), minimum, and maximum will be presented for the annualized rate of events and number of priapic events at Baseline, by Week 26 and by Week 52 .

The change from baseline in rates of events at Week 26 (i.e. evaluation at Week 27, Day 1) and Week 52 (i.e. evaluation at Week 53, Day 1) will be summarized by n, mean, median, standard deviation (SD), lower quartile (Q1), median, upper quartile (Q3), and minimum and maximum.

Graphical representation of annualized rates, through box plots or bar graphs or swimmer plot, as appropriate, will also be performed.

The Annualized Rates of Events at Week 26 (i.e. evaluation at Week 27, Day 1) and Week 52 (i.e. evaluation at Week 53, Day 1) will be summarized by n, mean, standard deviation (SD), lower quartile (Q1), median, upper quartile (Q3), standard deviation and minimum and maximum.

Additionally, cumulative number of acute priapic events, uncomplicated and complicated VOC events will also be summarized over time (like 0-12 weeks, 0-26 weeks, 0-40 weeks and 0-52 weeks).

Subgroup analyses displaying annualized rate, for complicated and uncomplicated VOC events will be performed based on use of hydroxyurea versus no use of hydroxyurea by 26 weeks and 52 weeks.

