2.7.1 Adverse events (AEs)

For reporting of AEs, the overall observation period will be divided into three mutually exclusive segments:

1. Pre-treatment period: from day of subject's informed consent to the day before first dose of study medication
2. On-treatment period: from day of first dose of study medication to 105 days after last dose of study medication (or until EOT date for subjects continuing crizanlizumab after their EOT via commercial supply)
3. Post-treatment period: starting at Day 106 after last dose of study medication (or after EOT date for subjects continuing crizanlizumab after their EOT via commercial supply or a post-trial access program)

Reporting of AEs will be based on MedDRA version 25.0 or higher and the Common Terminology Criteria for Adverse Events (CTCAE) version 5.0 or higher.

AE summaries will include all AEs occurring during on-treatment period. All AEs collected in the AE CRF page will be listed along with the information collected on those AEs e.g. AE relationship to study drug, AE outcome etc. AEs outside of on-treatment period will be flagged in the listings.

Summary tables for AEs will include only AEs that started or worsened during the on-treatment period, the treatment-emergent AEs. The incidence of TEAEs (new or worsening from baseline) will be summarized by system organ class and or preferred term, severity (based on CTCAE grades), type of AE, relation to study treatment.

AEs will be summarized by number and percentage of subjects having at least one AE, having at least one AE in each primary system organ class (SOC) and for each preferred term (PT) using MedDRA coding. A subject with multiple occurrences of an AE will be counted only once in the respective AE category. A subject with multiple CTCAE grades for the same preferred term will be summarized under the maximum CTCAE grade recorded for the event. AE with missing CTCAE grade will be included in the 'All grades' column of the summary tables.

In AE summaries, the primary system organ class will be presented alphabetically and the preferred terms will be sorted within primary SOC in descending frequency. The sort order for the preferred term will be based on their frequency in all subjects.

Serious adverse events will be tabulated. All deaths (on-treatment death and post-treatment death) will be summarized.

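### Crises exempted from AE/SAE reporting as efficacy endpoints have no direct VOC summary if they occur in early stoppers (on the completer reading) or late after the last dose

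*SAP*

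**What the plan says.** **Exemption.** Protocol 10.1.2 gives the rule and its reason together: "VOCs are considered secondary endpoints for the purpose of evaluation of efficacy, AEs and SAEs involving VOCs SHOULD NOT be reported as AEs". Table 10-1 lists uncomplicated pain crisis, acute chest syndrome, hepatic and splenic sequestration, and "Acute priapism requiring a visit to a medical facility". Procedures that belong to a crisis, such as ventilation in acute chest syndrome, are also kept off the AE record.

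**Population.** SAP 2.2 sets the general rule: "All efficacy analyses will be performed on subjects in FAS who have completed treatment". SAP 2.6.1 applies it to the secondary endpoints: "The following secondary efficacy endpoints will be analyzed on all FAS subjects who have completed 26 and 52 weeks on treatment". Protocol 12.5.1 names 52-week completers only, and SAP Section 4 records the change. SAP 2.6.2 reads differently. It refers the acute priapism analysis to the full analysis set (FAS), handled like the primary endpoint, and says the annualized rate allows for early dropouts by extrapolating each subject's rate to a year.

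**Windows.** In SAP 2.6.2 the rate's "end date is defined as the minimum of (last dose date until treatment discontinuation + 27 days", or the date of a change in sickle cell therapy or the cut-off if earlier. In SAP 2.1.1 the by-Week-52 window closes the day before the Week 53 visit. The longest cumulative VOC count in SAP 2.6.2 covers weeks 0 to 52. For AEs, SAP 2.7.1 has "On-treatment period: from day of first dose of study medication to 105 days after last dose of study medication", or to the end-of-treatment (EOT) date for subjects who move to commercial supply.

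**Back-up analyses.** SAP 2.6.3 to 2.6.6 (intercurrent events, missing values, sensitivity and supplementary analyses for secondary endpoints) are all marked as not applicable, as is SAP 2.7.1.1 on AEs of special interest. The visible text of SAP 2.7 contains no VOC table.

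**The concern.** The exemption is sound only if the efficacy tables pick up what the safety tables drop. The safety tables cover everyone dosed, to 105 days after the last dose. The efficacy tables cover fewer subjects, at least on the SAP 2.2 and 2.6.1 reading, and a shorter time. Whatever lies between the two has no direct summary.

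The events concerned are among the most serious that these patients have. The subjects affected are those who stopped early, who may have done worse, and the time affected is the period after drug is withdrawn, when any rise in crises would appear. With 36 subjects and no control arm, one or two unreported cases of acute chest syndrome or acute priapism would change how the safety section reads.

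**Working it through.** **1. The plan's own figures.** The sample size section gives 34 evaluable subjects. A one-sample t-test with difference 2.5 (25% of a baseline rate of 10.0), SD 5.0 and two-sided alpha 0.05 has 80.8% power at n = 34, in line with the stated 80%. With 5% dropout, 34 / 0.95 = 35.8, so 36 are enrolled. Planned early stoppers: 36 - 34 = 2 (equivalently 36 x 0.05 = 1.8). This figure belongs to the 26-week primary analysis. The documents give no planned number stopping between Weeks 26 and 52.

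**2. Day arithmetic.** SAP Table 2-1 uses target day = (week - 1) x 7 + 1. The last planned infusion is at Week 51 (Protocol 6.1).

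| Boundary, dosing to Week 51 | Calculation | Day |
|---|---|---|
| Last infusion | 50 x 7 + 1 | 351 |
| By-Week-52 window closes (nominal) | 52 x 7 + 1 - 1 | 364 |
| Rate window closes | 351 + 27 | 378 |
| AE on-treatment period closes | 351 + 105 | 456 |

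The tail covered for AEs but not for VOC rates is Days 379 to 456: 105 - 27 = 78 days, and 78 / 105 = 74%. Measured from the by-Week-52 window it is 456 - 364 = 92 days. Both apply only to subjects who have the 105-day follow-up. Subjects moving to commercial supply leave the AE period at EOT.

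**3. An early stopper.** Take a last dose at Week 15 (Day 99). AEs are summarized to Day 99 + 105 = 204.
- Completer reading (SAP 2.2, 2.6.1): none of this subject's VOCs enter a VOC table.
- FAS reading (SAP 2.6.2): VOCs enter the rate to Day 99 + 27 = 126. Days 127 to 204 are again 78 days outside the rate. The cumulative counts state neither a population nor a stopping rule, so on this reading they might include those days.

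**4. A subject who stops between Weeks 26 and 52.** He has completed 26 weeks, so his crises to Week 26 are in the by-26 tables. On the completer reading his later crises are not in the by-52 tables.

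**5. Is there a second route?** A non-fatal acute chest syndrome that leads to stopping is not an AE, so it is absent from the SAE table and from the summary of AEs leading to discontinuation. Sensitivity analysis 2 (SAP 2.5.5) uses data after discontinuation, but only for priapic events to Week 26. Acute priapism could be counted there; acute chest syndrome, sequestration and pain crises could not.

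**6. Are the data there?** Protocol Table 8-2 requires VOC information whenever a crisis occurs in treatment or follow-up. Protocol 9.1.1 sets the minimum after discontinuation as new or concomitant treatments and AE/SAE, which by the exemption leaves VOCs out. The two do not agree.

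**The case against.** A reader might infer that these crises appear nowhere in the report. The documents do not support that. SAP 2.1.1 puts all available data into listings. SAP 2.7.2 summarizes all deaths. Protocol 10.1.2 keeps complications that are not themselves VOCs in AE/SAE reporting. Reasons for discontinuation are tabulated on the FAS (SAP 2.3.1), and rescue medication for VOC is summarized like concomitant medication, on the Safety Set (SAP 2.4.2). Some sections of both documents are redacted, including text about VOCs in Protocol 8.4.2, and a further summary there cannot be excluded.

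A reader might also infer that everyone who stops before Week 52 loses all crises, or that the 78-day tail applies to every subject. Neither holds: the by-26 tables cover 26-week completers, and subjects moving to commercial supply have no 105-day tail. The by-Week-52 window also follows the actual visit date, and SAP Table 2-1 lets the EOT window extend to Day 447, so a late visit could bring part of the tail into a count.

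The strongest objection is that SAP 2.6.2 may be meant to include early stoppers. If so, their crises to last dose + 27 days are in the rates and the first gap closes. But that contradicts SAP 2.2 and 2.6.1, so the text still has to be settled, and the rates still stop 78 days before the AE period does. The other outputs are real but indirect: a listing or a rescue-medication table does not say how many subjects had acute chest syndrome.

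It is also fair that the exemption is a programme-wide choice, that VOCs have their own objectives, and that without a control arm a rise after treatment could only be described.

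**Conclusion.** The point holds in a limited form. In the visible text, two groups of non-fatal exempt crises have no direct VOC summary:

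- On the completer reading, all crises in subjects who stop before Week 26 (about 2 of 36 at the planned 5% dropout), and crises after Week 26 in subjects who stop between Weeks 26 and 52.
- On either reading of the population, crises later than last dose + 27 days are outside the rates (earlier still after a change in sickle cell therapy). On the nominal schedule with dosing to Week 51 they are outside the counts too. This is 78 of 105 days for subjects who have the 105-day follow-up.

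No number of missed crises is given, because the documents state no VOC rate and no dropout rate beyond Week 26. The conclusion assumes that no redacted section supplies the summary. The primary result is not affected. This should be fixed because it changes what the safety report shows, but it does not undermine the trial's main analysis.

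**What to change.** 1. State one population for the secondary endpoints and reconcile SAP 2.2 and 2.6.1 with 2.6.2.
2. Add to SAP 2.7 a Safety Set table of VOCs by type (uncomplicated crisis, acute chest syndrome, hepatic sequestration, splenic sequestration, acute priapism), regardless of treatment completion. Run it from first dose to last dose + 105 days, or to EOT for subjects moving to commercial supply, split at last dose + 27 days. Show subjects with at least one event, number of events, exposure-adjusted rate, hospitalisation, and events leading to discontinuation.
3. Reconcile Protocol Table 8-2 with the minimum post-discontinuation data in Protocol 9.1.1, and report for how many early stoppers VOC information was actually collected after treatment.

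The cost is one descriptive table from the existing VOC eCRF page. Whether it needs no new data depends on item 3: if VOCs were not collected after discontinuation, the table will be incomplete for early stoppers and should say so.

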2.6.2 Statistical hypothesis, model, and method of analysis

Similar analyses on percent reduction in acute priapic events for subjects from full analysis set will be conducted, as done for primary endpoint.

Annualized rates will be calculated for the secondary endpoints.

The annualized rate of events is defined as the total number of events for a subject occurring from the date of initial infusion to the last contact date of the Treatment Phase of the study x 365.25 divided by the number of days during that same time period. This calculation accounts for early dropouts or lost to follow-up by extrapolating the priapism events rate of every subject to 1 year.

Annualized events rate = Total number of events x 365.25 / (end date – treatment start date +1), where end date is defined as the minimum of (last dose date until treatment discontinuation + 27 days, date of initiation or discontinuation of HU/HC or L-glutamine - or other therapies to treat SCD and or to prevent/reduce VOCs such as voxelotor and erythropoietin, cut-off date).

Descriptive summary statistics including n, mean, standard deviation (SD), lower quartile (Q1), median, upper quartile (Q3), minimum, and maximum will be presented for the annualized rate of events and number of priapic events at Baseline, by Week 26 and by Week 52 .

The change from baseline in rates of events at Week 26 (i.e. evaluation at Week 27, Day 1) and Week 52 (i.e. evaluation at Week 53, Day 1) will be summarized by n, mean, median, standard deviation (SD), lower quartile (Q1), median, upper quartile (Q3), and minimum and maximum.

Graphical representation of annualized rates, through box plots or bar graphs or swimmer plot, as appropriate, will also be performed.

The Annualized Rates of Events at Week 26 (i.e. evaluation at Week 27, Day 1) and Week 52 (i.e. evaluation at Week 53, Day 1) will be summarized by n, mean, standard deviation (SD), lower quartile (Q1), median, upper quartile (Q3), standard deviation and minimum and maximum.

Additionally, cumulative number of acute priapic events, uncomplicated and complicated VOC events will also be summarized over time (like 0-12 weeks, 0-26 weeks, 0-40 weeks and 0-52 weeks).

Subgroup analyses displaying annualized rate, for complicated and uncomplicated VOC events will be performed based on use of hydroxyurea versus no use of hydroxyurea by 26 weeks and 52 weeks.

As appropriate, the estimated median change from Baseline at 26 weeks (i.e. evaluation at Week 27, Day 1) and 52 (i.e. evaluation at Week 53, Day 1) weeks in acute priapic events with associated 95% CI using a Hodges-Lehmann estimate will be reported. The median percent reduction will also be presented by Week 26 and Week 52.

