## 5.2 Exclusion criteria

Subjects meeting any of the following criteria are not eligible for inclusion in this study.

1. Patients who have penile prosthetic implants. Shunts or any other surgical procedure on the penis performed within 12 months prior to consenting are not allowed.
2. Patients who have taken drugs/medications that may induce priapism (as per [Appendix 5](#)) over the 14 weeks pre-screening period
3. Patients who have received leuprolide acetate (Lupron) or any other gonadotropin-releasing hormone receptor (GnRHR) agonist agents within 3 months before pre-screening.
4. Patients who had an erection lasting more than 12 hours over the 14 week pre-screening period
5. Patients who had an erection lasting more than 12 hours during the 12 weeks of the screening period
6. History of severe hypersensitivity reaction to other monoclonal antibodies, which in the opinion of the investigator may pose an increased risk of serious infusion reaction
7. Contraindication or hypersensitivity to any drug or metabolites from similar class as study drug or to any excipients of the study drug formulation
8. Received crizanlizumab
9. Received a monoclonal antibody or immunomodulatory agent within 1 year of screening, or has documented immunogenicity to a prior biologic
10. Received other selectin inhibitor or plans to receive it during the duration of the study
11. Patients should not be receiving another investigational trial within 30 days (or 5 half-lives of that agent, whichever is greater) prior to Screening or plans to participate in another investigational drug trial
12. History of familial long QT syndrome or know family history of Torsades de Pointes
13. History or current diagnosis of ECG abnormalities indicating significant risk of safety such as:

- Concomitant clinically significant cardiac arrhythmias (e.g ventricular tachycardia), and clinically significant second or third degree AV block without a pacemaker

14. Subjects with evidence of current alcohol/drug abuse:

15. Any documented history of a clinical stroke or intracranial hemorrhage, or an uninvestigated neurologic finding within the past 12 months before screening. Silent infarct only present on imaging is not excluded

16. Clinically significant bleeding disorder

17. Planning to undergo a major surgical procedure during the duration of the study

18. Patient with active HIV infection (detectable viral load)

19. Patients with active Hepatitis B infection (HBsAg positive)  

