2.2.1 Subgroup of interest

- The primary analysis will be conducted on a subgroup of subjects with stuttering (duration of priapic events from 1 to <=4 hours) and acute priapism. Acute priapic events are defined as an unwanted, painful erection that lasts more than 4 hours and need a visit to emergency room.

- Additional subgroup analysis will be performed based on duration of priapic events (i.e., <1, 1 to ≤4, >4 to ≤6, >6 to ≤12, >12 hours).
- Subgroup analysis of the primary endpoint will also be performed based on the number of priapic events categories (i.e. <7, 7 – 13, 14 – 21, ≥ 22) at baseline (12 weeks) and baseline (adjusted for 26 weeks). The priapic events categories may be re-grouped to ensure that there is adequate number of subjects in each category for analysis.
- Note that, subgroup analyses of the primary endpoint by age group will only be performed if an adequate number of subjects are present in each subgroup class.

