2.5.1 Primary endpoint(s)

The primary endpoint of the study is percent reduction from baseline in priapism events by 26 weeks (i.e., up to pre-infusion Week 27 Day 1). Priapism event is defined as unwanted, or painful erection lasting at least 60 minutes, self-reported.

Percentage change from baseline = (Post baseline value –Baseline value) * 100 / Baseline value; (relative change from baseline).

Percentage reduction from baseline is the negative percentage change from baseline.

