2.5.2 Statistical hypothesis, model, and method of analysis

It is expected that crizanlizumab treatment reduces priapic events by at least 25% in SCD subjects with priapism.

Demonstration of significant percent reduction from baseline in priapic events will be evaluated using following hypothesis:

$H_0: p < 0.25$, where p is the percent reduction in priapic events by 26 weeks.

$H_1: p \geq 0.25$, where p is the percent reduction in priapic events by 26 weeks.

If the above null hypothesis is rejected, significant reduction in priapic events will be demonstrated statistically.

Assuming uniformity in the occurrence of priapic events before exposure to crizanlizumab treatment, baseline will be adjusted for 26 weeks for analysis purpose.

Baseline (adjusted for 26 weeks): Number of priapic events in 12 weeks screening period * (26/12) and percentage change from baseline = (Post baseline value –Baseline (adjusted to 26 weeks) value) * 100 / Baseline (adjusted to 26 weeks) value.

Percentage reduction from baseline is the negative percentage change from baseline.

Percent reduction from baseline in priapic events will be tested using a non-parametric test (i.e., Wilcoxon's Sign Rank test) and p-value will be reported. The study would be declared a success, if percentage reduction in events is $\geq 25\%$ and $p < 0.05$ is obtained from Wilcoxon's Sign Rank test.

Hodges-Lehmann estimate of median percent reduction in priapic events will also be reported, along with corresponding 95% confidence intervals.

Number of priapic events will be summarized at baseline (adjusted for 26 weeks) and by Week 26, and percent reduction from adjusted baseline by Week 26 will be summarized by n, mean, standard deviation (SD), lower quartile (Q1), median, upper quartile (Q3), minimum and maximum.

Graphical representation of percentage reduction, through box plot or bar graph or waterfall plot, will be performed as appropriate by 26 weeks.

In addition, subgroup analysis of the primary endpoint will be performed based on the number of priapic events categories (i.e. <7, 7 - 13, 14 - 21, \geq 22) at baseline (12 weeks) and baseline (adjusted for 26 weeks). Additional analyses of the primary endpoint will also be performed for the subgroups of subjects with stuttering and acute priapism. Summary statistics for percentage reduction by 26 weeks will be presented for each subgroup.

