2.5.6 Supportive analyses

The supportive analyses described below will be performed on all FAS patients who have completed 26 weeks on treatment. Missing values will be imputed as stated in [Section 2.5.4](#)

Supportive analysis 1:

Annualized priapic Events Rate: The annualized rate of priapic events is defined as the total number of priapic events for a subject occurring from the date of initial infusion to the last contact date of the Treatment Phase of the study \times 365.25 divided by the number of days during that same time period. This calculation accounts for early dropouts or lost to follow-up by extrapolating the priapism events rate of every subject to 1 year.

Supportive analysis 2:

Percent reduction from baseline in priapic events will also be assessed by Week 52. Assuming uniformity in the occurrence of priapic events before exposure to crizanlizumab treatment, baseline will be adjusted for 52 weeks for analysis purpose.

Baseline (adjusted for 52 weeks): Number of priapic events in 12 weeks screening period \times (52/12) and percentage change from baseline = (Post baseline value – Baseline (adjusted to 52 weeks) value) \times 100 / Baseline (adjusted to 52 weeks) value.

Percentage reduction from baseline is the negative percentage change from baseline.

Supportive analysis 3:

The total number of priapic episodes in the screening period (12 weeks baseline) will be compared to the total number of priapic episodes occurring in the first 12 weeks on treatment (0-12 weeks) using a nonparametric test (i.e. Wilcoxon's Sign Rank test). Additionally, a similar analysis will be performed to compare to the total number of priapic episodes occurring in the last 12 weeks on treatment (15-26 weeks). For the analysis purpose, for 0-12 weeks: Day 1 to Day 84 and for 15-26 weeks: Day 105 to Day 182 will be used.

Supportive analysis 4:

Number of priapic events will be summarized in the screening period (12 weeks baseline), in first 12 weeks on treatment (0-12 weeks), and in the last 12 weeks on treatment (15-26 weeks) and percent reduction from baseline will also be summarized. For the analysis purpose, for 0-12 weeks: Day 1 to Day 84 and for 15-26 weeks: Day 105 to Day 182 will be used.

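### Percent reduction in acute priapic events has no value for subjects with no acute event at baseline, so this secondary endpoint is biased towards benefit when acute events are rare

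*SAP*

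**What the plan says.** Percent reduction from baseline in acute priapic events by 26 and 52 weeks is a named secondary endpoint (protocol Table 2-1 and 12.5.1b; SAP Table 1-1 and 2.6.1b). An acute event is an erection of about 4 hours or longer that also leads to an emergency-room visit.

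For its analysis, SAP 2.6.2 states "Similar analyses on percent reduction in acute priapic events for subjects from full analysis set will be conducted, as done for primary endpoint", and protocol 12.5.2 says the same. The formula carried over is "Percentage change from baseline = (Post baseline value –Baseline value) * 100 / Baseline value" (SAP 2.5.1). SAP 2.5.2 applies it to a scaled baseline, "Post baseline value –Baseline (adjusted to 26 weeks) value) * 100 / Baseline (adjusted to 26 weeks) value", where the scaled baseline is "Number of priapic events in 12 weeks screening period * (26/12"). SAP 2.5.6 scales all priapic events in the same way for the longer period: "baseline will be adjusted for 52 weeks for analysis purpose".

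Amendment 4 of the SAP added one condition to the acute endpoint: "Note that, this analysis will only be performed if an adequate number of subjects are present". No threshold is given. SAP 2.6.3 to 2.6.6, which would cover intercurrent events, missing values and sensitivity analyses for secondary endpoints, are marked not applicable.

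**The concern.** The formula is safe for the primary endpoint, because inclusion criterion 5 requires at least 3 events of 60 minutes or more in the 12-week screening period. No criterion requires an acute event. Protocol 1.1.2 reports that most affected patients had repeated events lasting under 3 hours, so baseline acute counts of 0 are to be expected. Scaling by 26/12 or 52/12 leaves 0 at 0.

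The resulting omission runs in one direction. A subject with a zero baseline can only stay at zero or get worse, and he contributes nothing. A subject who contributes had at least one acute event in a short window, so his count tends to fall back whether or not the drug works. With no control arm, nothing offsets this. At stake is the headline figure for the gravest form of priapism that the study measures.

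**Working it through.** **The plan's own figures.** The documents give no rate, effect size or power for acute events. The only sample-size figure belongs to the primary endpoint: a difference of 2.5 (25% of 10.0), SD 5.0 and two-sided 0.05 give n = 34 with power 0.81 by one-sample t test, and 34/0.95 = 35.8, so 36 enrolled. It reproduces, and is used here only to set the trial size at 34.

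**One baseline event.** The scaled baseline is 1 x 26/12 = 2.17. On-treatment counts of 0, 1, 2 or 3 over 26 weeks give reductions of 100%, 53.8%, 7.7% and -38.5%. Two acute events on treatment still score as a reduction. **No baseline event:** the denominator is 0, and there is no value for any on-treatment count.

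**Inactive drug.** Assumptions:
- Each subject has the same rate before and during treatment.
- Baseline count is Poisson(λ) over 12 weeks, and the 26-week count is Poisson(λ x 26/12).
- λ is either equal for all subjects or gamma-distributed with shape k = 1 or 0.5.
- The mean of λ, written μ, is assumed.

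Share of subjects with a defined value:
- equal rates: 1 - exp(-μ)
- gamma: 1 - (1 + μ/k)^(-k)

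Share of all on-treatment acute events that fall in undefined subjects:
- equal rates: exp(-μ)
- gamma: (1 + μ/k)^(-(k+1))

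At μ = 0.25 the defined shares are 1 - exp(-0.25) = 22%, 1 - 1/1.25 = 20% and 1 - 1.5^(-0.5) = 18%. The shares of events lost are 78%, 1.25^(-2) = 64% and 1.5^(-1.5) = 54%.

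Medians come from simulated 34-subject trials. Ranges run over the three rate patterns.

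| Mean acute events per 12 weeks | Subjects defined | Typical median reduction | On-treatment acute events in undefined subjects | Chance that the median is 25% or more |
|---|---|---|---|---|
| 0.25 | 18-22% | 54-100% | 54-78% | 0.91-1.00 |
| 0.5 | 29-39% | 54% | 35-61% | 0.83-0.99 |
| 1.0 | 42-63% | 31-42% | 19-37% | 0.58-0.74 |
| 2 | 55-86% | about 8-14% | 9-14% | 0.15-0.31 |
| 3-5 | 62-99% | about -2% to 8% | 1-6% | 0.00-0.17 |

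At a mean of 0.5, some 8 to 14 of 34 subjects have no acute event at baseline but at least one by Week 26, and none of them enters the endpoint.

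**The test.** Suppose the primary rule were carried over as a median of at least 25% with signed-rank p < 0.05 against zero, in trials with 6 or more defined subjects. An inactive drug then meets it with probability 0.61-0.98 at 0.25, 0.39-0.95 at 0.5, 0.18-0.50 at 1.0 and at most 0.09 at 2.

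**52 weeks** (equal rates and shape 0.5). Medians are 65-77% at 0.25, 49-54% at 0.5, 31% at 1.0 and 8-15% at 2.

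**All subjects kept.** Total on-treatment events divided by total baseline events x 26/12 stays close to 1.00 at every assumed rate, and the median absolute change at 26 weeks lies between 0 and -0.25 events. The artefact therefore comes from the denominator.

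**The case against.** The strongest reply is that the SAP does not rely on percent reduction alone. Section 2.6.2 plans, without condition, annualised rates for the secondary endpoints, change from baseline in rates, and cumulative acute-event counts over 0-12, 0-26, 0-40 and 0-52 weeks. Endpoint (d) in 2.6.1 counts acute priapism among complicated VOCs. All of these can be computed for subjects with a zero baseline. This stands. A reader might infer that new or worsening acute priapism would go unseen in the report, and the documents do not support that.

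Three further points on that side also stand:
- **Retained subjects can worsen.** Up to about 31% of them do at assumed means up to 1.0. The selection removes those who cannot improve; it does not leave only those who must.
- **The size depends on an assumed rate.** At 2 or more acute events per 12 weeks the bias is small. The 100% median arises with only 7 or 8 of 34 subjects defined, which is where the Amendment 4 condition is most likely to stop the analysis.
- **The stated success rule concerns the primary endpoint,** whose denominator cannot be 0. This defect cannot produce a false declaration of study success.

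A reader might also infer that percent reduction in the class above 12 hours can never be calculated. SAP 2.2.1 says "Additional subgroup analysis will be performed based on duration of priapic events", and exclusion criterion 5 removes "Patients who had an erection lasting more than 12 hours during the 12 weeks of the screening period". The inference holds only if the classes sort events. If they sort subjects, the endpoint is still all priapic events and the denominator is at least 3. The text does not say which, so the fair criticism is ambiguity.

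Two replies do not stand. The Amendment 4 condition decides whether the analysis is run, not who is in it. Nor does the Poisson imputation help: SAP 5.4.1 fills in missing on-treatment counts, whereas here both counts are observed and the ratio does not exist.

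**Conclusion.** The concern holds for the percent-reduction endpoint in acute priapic events, its median and its test, and for nothing wider. The SAP does not state that subjects with a zero baseline are excluded. The exclusion follows from dividing by zero with no rule for that case.

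The direction is towards apparent benefit. The size rests on an acute rate that the documents do not give. It is large at about 1 or fewer acute events per 12 weeks (typical median reductions of 31-100% from an inactive drug) and small at 2 or more. The 4-hour and emergency-room requirements, with the protocol's remark on typical duration, make low rates plausible but do not establish them. The calculations also assume a constant rate per subject and Poisson counts. Because this is a secondary endpoint in a single-arm phase II study, the change should be made but does not threaten the primary conclusion.

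**What to change.** In SAP 2.6.2, recorded in SAP section 4 as a change to the protocol-specified analysis:

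1. Make the main acute-priapism analysis the within-subject change in acute-event rate (on-treatment minus scaled baseline) in all subjects of the analysis set, zeros included.
2. Add the pooled ratio of on-treatment to baseline acute events per person-week, with a confidence interval that treats the subject as the unit.
3. Add a table of baseline none/any by on-treatment none/any.
4. If percent reduction is still shown because the protocol names it, label it descriptive, restrict it to subjects with a baseline acute event, give the number undefined and their on-treatment acute events, and do not test it.
5. In SAP 2.2.1, state whether the duration classes sort subjects or events. If events, report the class above 12 hours as on-treatment counts only.

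No new data are needed. The cost is SAP text, a few re-specified tables and a documented departure from a measure that the protocol names. The reported figure is likely to be less favourable if acute events are rare. The change removes the selection made by the formula. It does not supply a control arm, nor remove any fall-back caused by requiring 3 priapic events in screening.
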